If in the period from 2 to 12 weeks a participant falls ill with influenza/ARVI¹, then he prematurely completes participation in the study (as having reached the primary endpoint). A participant is considered fallen ill with influenza/ARVI if the doctor identifies the following symptoms: febrile/subfebrile body temperature, presence at least one flu-like nonspecific symptom (decreased activity/impaired behavior/weakness; headache; chills) and at least one respiratory symptom (runny nose; nasal stuffiness; hoarseness/husky voice; sore throat; cough). In this case, the doctor makes an unscheduled visit (at home or in a medical center), which is final. During the visit, the doctor carries out the procedures of Visit 4. A nasopharyngeal swab is taken to identify the most common pathogens of influenza/ARVI².

If ARVI/influenza occurs within the first seven days from the onset of preventive therapy, the disease will not be recorded as an adverse event and will not be taken into account to evaluate the efficacy of the study drug, since an early manifestation of influenza/ARVI may indicate that the participant was included in the study when he/she was in the incubation period of an infectious disease.

During the study, concomitant therapy for underlying chronic conditions, as well as routine vaccination of the participant, are allowed, with the exception of the drugs indicated in the section "Prohibited Concomitant Treatment".

Inclusion and exclusion criteria

Inclusion criteria

- 1. Children of either gender aged from 1 month to 6 years old³.
- 2. The absence of clinical symptoms of any infectious disease, but not earlier than 14 days from its onset.
- 3. Seasonal rise in ARVI incidence, confirmed by official information.
- 4. An information sheet (Informed Consent form) for the subject participation in the clinical trial signed by one parent/adopter of the patient.

Exclusion criteria

 Acute or subacute period of infectious disease of any etiology (viral, bacterial, fungal, etc.) and localization (including upper and lower respiratory tract infection, meningitis, sepsis, otitis media, urinary tract infection, intestinal infection, etc.).

¹ The symptoms associated with teething or vaccination (post-vaccination reactions and complications) are not considered as manifestations of influenza/ARVI.

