- The patient's parent/adopter parent works for OOO "NPF "MATERIA MEDICA HOLDING" (i.e., the company's employee, part-time employee under contract or appointed official in charge of the trial, or their immediate family).

Discontinuation criteria

1. Failure or refusal of the child or his/her parents/adopters to comply with the protocol.

⁴ Primary and secondary immunodeficiencies, regardless of etiology, are characterized by persistent immunodeficiency. Transient immunomodulation do not represent immunodeficiency. Children with recurrent respiratory infections have transient immunomodulation. High rates of infectious diseases during the first years of life should not be considered as a pathology; this condition is not attributable to immunodeficiency and does not exhibit negative effect on immunity formation. Such subjects are eligible.

Subjects with immunodeficiency need complex therapy using the products forbidden within the study.

- 2. The necessity to use medications not permitted within the study.
- 3. An adverse event requiring discontinuation of the investigational product.
- 4. The desire of the child or parent/adoptive parent to complete the study ahead of schedule for any reason.
- 5. Cases not specified by the protocol, when the investigator decides that the further participation may harm the child.
- 6. Incorrect inclusion of ineligible child.
- 7. The patient did not pass the screening procedure.
 - 8. The participant got influenza/ARVI.

Number of subjects

1036 participants of both genders aged 1 month to 6 years old (518 participants in each group) are planned to be included and randomized in the clinical trial. It is estimated that approximately 880 children (440 participants in each group) will complete participation in the study in accordance with the protocol.

Interim analysis

Since the recruitment of participants covers more than one epidemic season, a blind intermediate analysis is carried out in each season (without revealing the participant's membership in one or another experimental group) to possibly clarify a priori research parameters.

Based on the results of a blind interim analysis, a significant difference between the base population frequency of the events studied and the planned one will be revealed, the sample size of the study is reassessed.

Treatment

Group 1

Name of the medicinal product: Anaferon for children

Active ingredient: affinity purified antibodies to human interferon-gamma – 0.003 g*

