* applied to lactose monohydrate as water ethanol mixture containing no more than 10^{-16} ng/g of active substance

Excipients: Lactose monohydrate 0.267 g, microcrystalline cellulose 0.03 g, magnesium stearate 0.003 g

Method of administration: Tablet for oral use. One tablet per intake, once daily (approximately at the same time).

The product is administered outside a meal (in the interval between meals or 15 min prior to meal or fluid intake), the tablets should be held in mouth until complete dissolution. For young

children (aged 1 month to 3 years old), the tablet is recommended to be dissolved in a small amount (1 tablespoon) of drinking water of room temperature.

Dosage form: Tablets.

Description: White to off-white, round, flat, scored on one side and beveled tablets. **Storage conditions:** Store at temperature below 25°C. Keep out of the reach of children.

Group 2

Name of the medicinal product: Placebo

Active ingredient: NA

Excipients: Lactose monohydrate 0.267 g, microcrystalline cellulose 0.03 g, magnesium stearate 0.003 g

Method of administration: Placebo using Anaferon for children scheme.

Dosage form: Tablets.

Description: White to off-white, round, flat, scored on one side and beveled tablets.

Storage conditions: Store at temperature below 25°C. Keep out of the reach of children

Treatment duration

Anaferon for children/Placebo treatment duration is 12 weeks.

Observation period

According to the protocol, the child's participation in the study lasts 12 weeks, including screening and randomization (the first day) and the period of study therapy (12 weeks).

Basic therapy

During the entire study period, the participant can receive therapy for the underlying and concomitant diseases that are not criteria for non-inclusion.

Prohibited concomitant therapy

Two weeks prior to enrollment and during the study the following drugs are prohibited:

- 1. Antivirals (J05), except for Anaferon for Children prescribed in this trial.
- 2. Immunostimulants (L03), including:
 - interferon inducers (acridonacetic acid, meglumine acridoacetate/cycloferon[®], umifenovir/arbidol[®], kagocel[®], tilorone/amixin[®], lavomax[®], tilaxin[®], polyadenylic acid + polyuridylic acid/poludan[®], oxodihydroacridinylacetate odium/neovir[®], ribonucleate sodium/ridostin, etc, deoxyribonucleate sodium/derinat[®] etc.)
 - interferons
 - bacterial immunomodulators (including ribomunyl[®], IRS-19, imudon[®],

broncho-munl^{\mathbb{R}} and etc.)

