- pidotimod/imunorix
- interleukins
- synthetic immunostimulants (levamisole, alpha-glutamyl-triptophan/thymogen, etc.)
- thymus hormone-containing drugs
- herbal immunostimulants (immunal[®], etc.)
- 3. Immunosuppressants (L04).
- 4. Antineoplastic agents (L01) and hormones (L02).
- 5. Immune sera and immunoglobulins (J06).
- 6. Fenspiride (R03DX03), omalizumab (R03DX05).
- 7. Systemic corticoids (H02AB).
- 8. Homeopathic drugs.
- 9. Drugs known to cause allergic reactions in the patient.

Study design scheme

Schedule of study procedures

| Procedure/visit | Visit 1 | Visit 2 «phone» | Visit 3 «phone» | Visit 4 |
|-----------------------------------|---------|-----------------|-----------------|------------------|
| | (Day 1) | (Week 4±3 days) | (Week 8±3 days) | (Week 12±3 days) |
| Obtaining signed informed consent | + | | | |

CONFIDENTIAL

Protocol No. MMH-AD-008 23-Aug-2018

| | | | | 20 1148 2010 |
|---|---|---|---|--------------|
| form (ICF) | | | | |
| Eligibility assessment | + | | | |
| Recording concomitant medications | + | + | + | + |
| Randomization and prescription of study therapy | + | | | |
| Study drug supply | + | | | |
| Drug accountability and return, assessment of treatment compliance | | | | + |
| Evaluation of treatment safety | + | + | + | + |
| Telephone survey | | + | + | |
| Collection of nasopharyngeal swabs for PCR diagnosis* | | * Performed in case the child falls ill with influenza/ARVI during unscheduled (additional) visit with Visit 4 procedures | | |

Statistical Analysis

Samples

Statistical analysis will be carried out in the following sets:

Total set includes all participants whose parents/adoptive parents signed the Informed Consent Form.

The sample including all enrolled and randomized subjects who received at least one dose of the study drug to be used for analysis of *safety and tolerability* (*Safety population*), as all adverse events identified after the study product administration were recorded.

Full Analysis Set consists of all enrolled and randomized patients, except for those who met at least one of the following criteria:

- 1) failure to meet inclusion/non-inclusion criteria;
- 2) subject failing to take any dose of the study drug;
- 3) absence of any data on the subject after randomization.

This is the best set for the Intention-to-treat method, so it will be used in the Intention-to-treat efficacy analysis of the test therapy.

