Per Protocol set. This sample includes all subjects who completed the therapy as per the study protocol, without any missing visits or major protocol deviations. This set will be used in the Per Protocol efficacy analysis of the test therapy.

Evaluation of sample size

The sample size was assessed in accordance with the following rules and assumptions:

- 1. Statistical assumptions:
 - 1.1 the power of statistical tests 'P = (1β) ' is 80% (the probability of correct rejection of the null hypothesis is 0.8)

- 1.2 the probability of type 1 error 'a' is less that 5% (the probability of false acceptance of the alternative hypothesis is less than 0.05);
- 1.3 statistical criteria of intergroup comparisons will be two-sided;
- 1.4 calculation of sample size is based on the assumptions on the expected effect declared in the primary efficacy endpoint;
- 1.5 ratio between Anaferon for children and placebo sample sizes is 1:1 (one Anaferon for children subject: one placebo subject).
- 1.6 statistical hypothesis will be as follows:

null and alternative hypothesis on Anaferon for children superiority using the dosing scheme specified:

in terms of Cox proportional hazard model,

H₀:
$$\ln(T_1/T_2) \le \delta$$

H₁: $\ln(T_1/T_2) > \delta$,

where T_1 – median influenza/ARVI time in Anaferon for children group;

T₂ – median influenza/ARVI time in placebo group;

 Δ , δ –minimum clinically relevant effect.

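### The plan does not separate stopping study drug from leaving the study, so its intention-to-treat analysis rests on an unstated, untested assumption about children who leave early

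*Combined protocol and SAP*

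**What the plan says.** **Discontinuation criteria.** One list of eight items serves two purposes. Criteria 1 to 3 concern treatment: non-compliance, a non-permitted medicine ("The necessity to use medications not permitted within the study"), and an adverse event for which the product must be stopped. Criteria 4, 7 and 8 concern the study itself: a family's wish to finish early, failed screening, and influenza/ARVI. Criteria 5 (possible harm, in the investigator's judgement) and 6 (a child wrongly included) complete the list.

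**Prohibited concomitant therapy.** The section opens "Two weeks prior to enrollment and during the study the following drugs are prohibited". The list includes antivirals, interferons, interferon inducers, systemic corticoids and homeopathic products.

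**Study design.** A child who falls ill gets an unscheduled visit and "then he prematurely completes participation in the study (as having reached the primary endpoint". Illness requires raised temperature, at least one nonspecific symptom and at least one respiratory symptom, identified by the doctor. This exit is an event, not censoring.

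**Planned contacts.** Study design and the Schedule of study procedures contain Visit 1, telephone surveys at Weeks 4 and 8, Visit 4 at Week 12, and the unscheduled illness visit. Nothing is planned for a child whose drug has been stopped.

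**Statistical Analysis, Samples.** The Full Analysis Set drops only ineligible children, those with no dose and those with no data after randomization; "so it will be used in the Intention-to-treat efficacy analysis of the test therapy". Evaluation of sample size, item 2, acknowledges right censoring. No section gives a censoring rule for early leavers, a missing-data rule for the secondary percentages, or a sensitivity analysis.

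**The concern.** An intention-to-treat estimate is meant to use outcomes whether or not the child kept taking the drug. If stopping the drug also ends observation, those outcomes are not collected, and the time-to-event analysis has to treat each early leaver as having the same later risk as children who stay.

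That is hard to accept for criterion 2. Several prohibited classes could be given for a respiratory illness, and routine contact between Visits 1 and 4 is two phone calls. A child could need such a medicine while symptoms are early or incomplete, or before the study doctor has seen the child. The child then leaves, and nothing in the plan allows a later qualifying illness to be recorded. If such exits differ between arms, the hazard ratio is biased. The secondary percentages (illness-free, antibacterial use, hospitalization) lose the same children and have no rule for them.

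**Working it through.** **Inputs from the plan**
- Illness by day 84: 65% active, 80% placebo (Evaluation of sample size, item 2).
- b = 0.425, δ = ln(42/36) = 0.154, d = 0.725, 437 events, 604 per-protocol children (same item).
- 80% power, 5% type 1 error, 1:1 allocation, and "statistical criteria of intergroup comparisons will be two-sided" (items 1.1 to 1.5).
- Withdrawal 15%, counting losses at screening and during the study (item 2). Number of subjects gives 518 falling to 440 per group: 78/518 = 15.1%.

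**Assumed, not in the documents:** the share f of withdrawals in each arm that is driven by respiratory illness.

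**1. The plan's own figure.** Events = (1.960 + 0.842)² / [(0.425 − 0.154)² × 0.25] = 7.849/0.01836 = 427.5; divided by 0.725 this is 589.6 children. Unrounded ln(55/36) and ln(42/36) give 431.7 and 595.5. Both pairs are within 3% of 437 and 604. Inflation: 604/0.85 = 711 (stated 710); 880/0.85 = 1035.3, rounded up to 1036 (as stated). No arithmetic error is at issue here.

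**2. Illness hazards.** λ = −ln(1 − P)/84: active 0.01250, placebo 0.01916 per day. HR = 0.652.

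**3. Withdrawal hazards.** Solve w/(λ + w) × [1 − exp(−84(λ + w))] = 0.15 in each arm: active 0.00322, placebo 0.00406 per day. This takes the whole 15% as withdrawal before illness, an upper bound.

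**4. HR if illness-driven withdrawals were counted as events.** HR = (λ_A + f_A·w_A)/(λ_P + f_P·w_P).

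| f active | f placebo | HR |
|---|---|---|
| 0 | 0 | 0.652 |
| 20% | 20% | 0.658 |
| 50% | 50% | 0.666 |
| 50% | 20% | 0.706 |
| 20% | 50% | 0.620 |

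For example, (0.01250 + 0.5 × 0.00322)/(0.01916 + 0.2 × 0.00406) = 0.01411/0.01997 = 0.706. An analysis that censors these children shows 0.652 in every row.

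**5. Distance from the margin.** Planned: −ln(0.652) − 0.154 = 0.273. In the 0.706 row: 0.348 − 0.154 = 0.194, a fall of 29%. With 437 events, Φ(√(437 × 0.25) × distance − 1.96) falls from about 81% to about 53%.

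**6. Secondary 12-week percentages, extreme bounds.** If 15% have unknown status and the rest fall ill at 65% and 80%, illness lies between 0.85 × 65% = 55.25% and 70.25% on active, and between 68% and 83% on placebo. The planned 15-point difference could then lie anywhere from −2.25 to +27.75 points.

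**7. Cost of continued observation.** If illness after stopping dilutes b by a share g, power = Φ(√(0.25 × 0.725 × N) × [0.425(1 − g) − 0.154] − 1.96). The documents give totals of both 1036 and 710, so both are shown.

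| g | N = 1036 | N = 710 |
|---|---|---|
| 0 | 96% | 87% |
| 5% | 93% | 81% |
| 10% | 88% | 74% |
| 15% | 81% | 65% |

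**The case against.** **The text never says that observation ends.** The list is headed only as discontinuation, criterion 3 refers only to the product, and the document calls itself a protocol summary, so its silence is weak evidence about any fuller text. This stands in part: the end of follow-up and the censoring are inferences. They are strong ones, because drug stops and study exits share one list and no contact is scheduled afterwards.

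**A reader might infer that the intention-to-treat analysis cannot be done.** The documents do not support that. Early stoppers stay in the Full Analysis Set and contribute time until they leave. The analysis runs; what is missing is a stated and tested censoring assumption.

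**A reader might infer that a child with a cold but no fever is a missed event.** That child does not meet the event definition, and a child who does meet it is counted. The exposure is limited to children who leave under criterion 2 before the definition is met or the doctor has seen them. The documents give no frequency for this.

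**A reader might infer that the bias could never be examined.** Concomitant medicines are recorded at every scheduled visit, and reasons for withdrawal could be tabulated by arm. That is a partial check. It would not show whether a qualifying illness followed.

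**The 15% is not a loss-to-follow-up rate.** It includes screening losses and inflates from the per-protocol number, a set that also drops children with missed visits or major deviations, some with known outcomes. A 50% v 20% split in a double-blind trial has no support in the documents. Both objections stand, so the hazard ratios are illustrations only.

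**Conclusion.** The point holds as a gap in the plan: it does not say whether outcome observation continues after drug stops, and it has no censoring rule or sensitivity analysis for early leavers. The declared intention-to-treat analysis therefore depends on non-informative censoring, which is doubtful for some exits under criterion 2.

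The size of any bias is unknown. With equal illness-driven shares the effect on the hazard ratio is close to nil; material bias needs an imbalance between arms, and its direction follows the imbalance. All the figures rest on constant hazards, on the whole 15% leaving before illness, and on counting every illness-driven withdrawal as an event, which is broader than the protocol's definition. This is a cheap improvement that should be made, not evidence that the primary result would be wrong.

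**What to change.** - Define stopping study drug and leaving the study separately. Leave the rules on when a child stops drug unchanged.
- For eligible children who stop drug under criteria 1, 2 or 3, and under criterion 5 where the investigator sees no harm in observation alone, keep the planned Week 4, 8 and 12 contacts and the unscheduled illness visit up to Week 12, with parental agreement. Count illness that meets the Study design definition in the Full Analysis Set.
- Censor at last contact only children whose family ends contact.
- Leave criterion 6 out, because the Full Analysis Set excludes ineligible children.
- Add one sensitivity analysis that counts withdrawal for a non-permitted medicine given for a respiratory illness as an event, labelled as going beyond the protocol's event definition.

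**Cost.** A wording change, a few extra contacts for at most about 15% of children, and one more analysis. Some families who refuse to comply will also decline contact. Illness after stopping may dilute the on-treatment effect (working, step 7); the Per Protocol analysis still addresses that effect.

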At that the expected median time to the disease in placebo group is **36** days, minimum clinically relevant difference is **6** days (therefore, minimum median time for superiority is **42** days). The scheduled effect is equal to **19** days (median time to the disease in Anaferon for children group is **55** days).

Thus, the intended effect in terms of Cox model will be $\mathbf{b} = \ln(56/36) = \ln(1.53) = 0.425$, minimum clinical effect will be $\delta = \ln(42/36) = 0.154$. Based on the assumptions on the effects we will also take the presumed total proportion of subjects falling ill during the study as equal to $\mathbf{d} = 0.725$. Therefore, sufficient number of influenza/ARVI cases required to reject null hypothesis is 437, the total required number of subjects (PP) is 604 (accurate value 602.75).

As the subject recruitment covers more than one epidemic season, **blind interim analysis** will be made in each season to assess nuisance parameters of the study.

According to the above mentioned statistical terms and assumptions, sample size of each group for the final analysis will be **302** subjects for each group (PP set is **604** in total).

Given potential withdrawal of at least **15%** of the subjects at the screening and during the study for various reasons, at least **355** subjects should be enrolled in each group (**710** subjects in total, see 1.9).

Interim analysis

The analysis is made in accordance with point 2 without unblinding the treatment group.

CONFIDENTIAL

Statistical criteria

All statistical calculations will be made using the following groups of statistical criteria:

- parametric to assess continuous and interval accidental values;
- non-parametric to obtain:
 - evaluations on equality/inequality of proportions of subjects compared for various visits,
 - analysis of frequencies in features compared, and
 - evaluation of continuous and interval accidental values in case of violation of requirement on normal sample distribution.

Parametric criteria will be checked for normality of the samples compared (Kolmogorov-Smirnov test).

The following *parametric methods and approaches* are suggested:

- To evaluate differences in continuous variables obtained in one group at two different visits – Student t-test for paired samples.
- For evaluation of time changes in parameters under comparison analysis of variance (ANOVA) or covariance (ANCOVA) analysis in a modification with repeated measurements (Repeated Measures).

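### Two current sample sizes are stated, 1036 randomised / 880 per protocol and 710 / 604, and only the smaller follows from the stated inputs

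*Combined protocol and SAP*

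**What the plan says.** All of the following stands as current text in the version dated 23 August 2018.

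- The section *Number of subjects* gives the planned size: "1036 participants of both genders aged 1 month to 6 years old (518 participants in each group) are planned to be included and randomized". It continues: "It is estimated that approximately 880 children (440 participants in each group) will complete participation in the study in accordance with the protocol".
- *Interim analysis*, directly below: a blinded analysis is made each season. If the observed event frequency differs significantly from the planned one, the text ends "will be revealed, the sample size of the study is reassessed".
- *Evaluation of sample size*, item 2: the calculation takes "the presumed total proportion of subjects falling ill during the study as equal to" 0.725, and concludes that the "sufficient number of influenza/ARVI cases required to reject null hypothesis is 437, the total required number of subjects (PP) is 604 (accurate value 602.75").
- Same item: "sample size of each group for the final analysis will be 302 subjects for each group (PP set is 604 in total"). After allowance for 15% withdrawal, "at least 355 subjects should be enrolled in each group (710 subjects in total, see 1.9").
- Same item, the effect size: "\ln(56/36) = \ln(1.53) = 0.425", next to stated medians of 55 and 36 days.

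**The concern.** Two sizes are given for one trial, and neither is marked as replaced. The enrolment figure of 355 per group is worded as a minimum, so 518 would satisfy it. The per-protocol figure for the final analysis is not worded that way, and it is 302 in one place and 440 in the other.

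Three things are at stake. First, a reader cannot tell which target governs the end of recruitment. Second, the larger figure has no derivation in the document, so the basis of the 1036 design cannot be checked. Third, the yearly blinded analysis compares the observed event frequency with a planned one, and d = 0.725 is the only planned overall proportion given. If 1036 already reflects a revised event proportion, that comparator is stale.

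**Working it through.** **Inputs.** From *Evaluation of sample size*, item 1: two-sided 5%, 80% power, 1:1 allocation. From item 2:

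- illness by day 84 of 65% (Anaferon for children) and 80% (placebo);
- medians of 55 and 36 days, and a minimum median for superiority of 42 days;
- b = 0.425, delta = 0.154, d = 0.725 (the mean of 0.65 and 0.80);
- withdrawal of 15%.

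**Formula 1.8.** n = (1.960 + 0.8416)² / [(b − delta)² × 0.25 × d]. The numerator is 7.849, so events = 7.849 / [0.25 × (b − delta)²] and n = events / 0.725.

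**Reproducing the plan's 604.**

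| Effects used | b − delta | Events | n per protocol |
|---|---|---|---|
| Printed 0.425 and 0.154 | 0.271 | 427.5 | 589.6 |
| ln(55/36) and ln(42/36) | 0.2697 | 431.7 | 595.5 |
| Ratios rounded to 1.53 and 1.17 | 0.268 | 436.3, so 437 | 437/0.725 = 602.76 |

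The third row recovers the plan's 437 events and, to rounding, its 602.75. Carrying the incidences (80%, 65%, and 75% for the 5-point margin) through without rounding gives 406.2 events and n = 560.3, which is further still from 880. Using 56/36 literally gives 379 events and n = 523, so the plan's 604 rests on 55/36 and the printed 56 looks like a misprint.

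**Withdrawal (item 1.9).** 302/0.85 = 355.3 and 604/0.85 = 710.6, printed as 355 and 710 (rounding up would give 356 per group, or 711 in total). 440/0.85 = 517.6, so 518 per group and 1036. Both pairs use the same 15%, so withdrawal does not explain the gap.

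**Size of the gap.** 1036 − 710 = 326 and 1036/710 = 1.459. 880 − 604 = 276 and 880/604 = 1.457.

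**Does any reading of the inputs give 880?** None of those tried does:

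- one-sided 5%: 464–475;
- 90% power: 789–807;
- no margin: 241–250;
- two proportions: 276, or 302 with continuity correction;
- two proportions with the 5-point margin: 608, or 814 at 90% power.

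**Power at each size.** Power = Phi[(b − delta) × √(events/4) − 1.96].

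- 604 × 0.725 = 438 events: 80.1% at 0.268, 80.9% at 0.271.
- 880 × 0.725 = 638 events: 92.3% at 0.268, 92.8% at 0.271.

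**What would produce 880 at 80% power?** Keeping 437 events, d = 437/880 = 0.497. With the other two effect values d is 0.486 (427.5/880) or 0.491 (431.7/880). Alternatively, keeping d = 0.725, b − delta = √[7.849/(0.25 × 638)] = 0.222. These are back-calculations; the document states none of these values.

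**Would changing d alone be coherent?** Under the plan's exponential model with the same hazard ratio, d = 0.497 implies incidences of about 57% and 42% and medians of about 69 and 106 days. Keeping the 6-day margin then gives delta = ln(1 + 6/69.0) = 0.083 and n of about 541. So 880 appears only if delta is held as a ratio (1.17) while the medians behind it move.

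**The case against.** The best defence is that 1036/880 is the output of the blinded reassessment. The protocol provides for one immediately below the figure, the 65%/80% incidences are introduced as what was initially assumed, and changing d alone to 0.497 while keeping 437 events and 15% withdrawal gives 880 and 1036. If so, the extra children are needed: at d = 0.497, 604 completers give about 300 events and about 64% power. It can also be said that 302 per group is conditional on the assumptions listed, that 880 is an estimate of completers and not a requirement, and that the document calls itself a protocol summary, so a fuller derivation may exist elsewhere.

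Much of this is fair. The two sizes are incompatible on the stated inputs, not under every set of inputs, and the extra 326 children cannot be called unnecessary. But the document does not report that a reassessment took place, does not give a revised d, and does not link one to 1036. If one did take place, the sample-size section still presents d = 0.725, the medians of 36, 42 and 55 days, 604 and 710 as working values, and they are superseded. An estimate of 880 completers where 604 are required also needs a reason, and none is given.

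**Conclusion.** The point holds. At least one size or one input in the current text is out of date. On the stated inputs the calculation supports about 604 per protocol and 710 randomised; 1036/880 exceeds this by 326 randomised and 276 per protocol. No loss of power follows from the stated inputs. If the true event proportion is near 0.497, the larger size is the one that restores 80% power with b and delta unchanged, and the printed derivation is the part that is wrong.

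This rests on formula 1.8 as printed, two-sided 5%, 80% power and the effects in item 2. The explanation by reassessment is an inference that cannot be confirmed from the document. The 56/36 misprint is minor and does not affect the size.

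**What to change.** State one size throughout.

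- If 1036/880 is current, rewrite item 2 of *Evaluation of sample size* with the d, incidences, medians, delta, event count and power that produce 880, restated together because they are linked through the exponential model. Say whether the margin is held in days or as a ratio. Give the source; if it is the blinded reassessment, give its date and the pooled event proportion observed. State the planned event proportion against which later blinded analyses will be compared.
- If 710/604 is current, correct *Number of subjects*.
- In either case, replace ln(56/36) with ln(55/36) if the 55-day median is kept.

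The cost is protocol wording and one recalculation. The correction itself adds no participants.
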